15.1 Adverse Events

Treatment emergent adverse events (TEAEs) are those events with onset dates occurring within the Treatment Period (see Section 9 for definition).

All analyses described in Section 15.1 will be based on TEAEs if not otherwise specified.

Incomplete AE-related dates will be handled as follows:

- In case the onset date is missing completely or missing partially but the onset month and year, or the onset year are equal to the start of study medication then the onset date will be replaced by the start date of study medication.
- In all other cases the missing onset day or missing onset month will be replaced by 1.
- Incomplete stop dates will be replaced by the last day of the month (if day is missing only), if not resulting in a date later than the date of subject's death. In the latter case the date of death will be used to impute the incomplete stop date.
- In all other cases the incomplete stop date will not be imputed.

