7.1 Schedule of Assessments

7.1.1 Screening (Month -1 to Baseline)

A complete Screening Evaluation is to be performed up to -1 month before Baseline. Screening will include the following assessments:

- Signing ICF
- Demographic data, including date of birth, gender and race
- Medical history, including concomitant medications and concomitant procedures
- Disease history, including classification of disease, number of relapses within the past 12 months, treatment history, diagnosis date
- Blood samples for serology and safety analysis at local laboratory (see [Section 7.4.3](#))*
- A lymphocyte count*** at local laboratory facilities
- Physical examination, including vital signs (blood pressure, heart rate, temperature)
- MRI assessment (see [Section 7.3.5](#))
- **CCI**
- The contraceptive method used will be recorded, or, alternatively, if applicable, the age at menopause will be captured
- Urine or serum pregnancy test (for WOCBP only) at local laboratory**
- Review of inclusion/exclusion criteria

***If the local laboratory blood test for serology and safety analysis mentioned at Screening visit is conducted within 10 days of the visit, no blood samples need to be repeated at Screening visit.**

****Additional serum or urine pregnancy tests will be permitted throughout the trial period as required by country specific regulations.**

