7.4.1.3 Definition of the Adverse Event Reporting Period

The AE reporting period for safety surveillance begins when the subject is initially included in the trial (date of first signature of informed consent/date of first signature of first informed consent) and continues until at end of month 24 as per the Final Visit guidelines.

Any SAE assessed as related to Mavenclad® must be reported whenever it occurs, irrespective of the time elapsed since the last administration of Mavenclad®.

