Treatment Period

The treatment period begins with the start of study medication on Study Day 1 and continues through to the completion of the treatment period at the Month 24 Visit (see protocol Section 7.1.3). Start of study medication is the date of first intake of study medication. Start of study medication in Year 2 is the date of first intake of study medication at or after the Month 12 Visit.

Treatment Period:

- Start = Start of study medication,
- End = Visit end date of Month 24 Visit or Early Termination (ET) Visit in case of early discontinuation, or the study discontinuation date, if the ET Visit was not performed.

Course 1 Treatment Period:

- Start = Start of study medication,
- End = Start of study medication at or after the Month 12 Visit -1 day or if the subject did not receive Treatment Course 2: Start of study medication of Treatment Course 1 + 457 days (which is obtained by 360 (12 months) + 90 (3 months) + 7 (visit window)), or date of the study discontinuation, if earlier.

Course 2 Treatment Period:

- Start = Start of study medication at or after the Month 12 Visit,
- End = End of Treatment Period.

Definition of Delayed Treatment Course 2

- The Treatment Course 2 will be defined as delayed, if the start of study medication is delayed by more than 3 months (=90 days) or did not start at all i.e.:
 - Start of Study Medication of Treatment Course 2 > Start of Study Medication of Treatment Course 1 + 457 days (which is obtained by 360 (12 months) + 90 (3 months) + 7 (visit window)), or
 - Treatment Course 2 never started (i.e. no study medication taken at or after the Month 12 Visit).

Data handling in case of a Delayed Treatment Course 2

For subjects with a Delayed Treatment Course 2, only data observed during the Course 1 Treatment Period will be analyzed in all efficacy analyses. Efficacy data after the Course 1 Treatment Period will be counted as missing in the statistical analyses and marked in the listings. In all efficacy analyses defined by Period, the subjects will be classified as if they discontinued at the end of the Course 1 Treatment Period. For subjects without a delay the whole Treatment Period will be analyzed.

For all other analyses (except efficacy) the data is not limited to the Course 1 Treatment Period for subjects with a Delayed Treatment Course 2.

Definition of start of COVID-19 pandemic

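### SAP 15.1 sets incomplete AE onset dates to the first-dose date without checking the stop date, so an event known to have ended before dosing can be counted as treatment-emergent

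*SAP*

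**What the plan says.** SAP Section 15.1 uses one criterion: "Treatment emergent adverse events (TEAEs) are those events with onset dates occurring within the Treatment Period". SAP Section 9 starts the Treatment Period with study medication: "Start of study medication is the date of first intake of study medication".

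Section 15.1 completes onset dates in two steps. If the date is wholly missing, or its known parts agree with the first-dose month and year, or with the first-dose year, "then the onset date will be replaced by the start date of study medication". Otherwise: "In all other cases the missing onset day or missing onset month will be replaced by 1". Stop dates have a separate rule: "Incomplete stop dates will be replaced by the last day of the month (if day is missing only"), limited by the date of death. Other incomplete stop dates stay as they are. No step compares onset with stop, or stop with first dose.

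Events before dosing are in the data by design. Protocol 7.4.1.3 states: "The AE reporting period for safety surveillance begins when the subject is initially included in the trial (date of first signature of informed consent"). On the length of that window, Protocol 7.1.1 states: "A complete Screening Evaluation is to be performed up to -1 month before Baseline". Screening can be prolonged case by case with the Medical Monitor's prior written approval.

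Unless otherwise specified, every analysis in SAP 15.1 is based on TEAEs. Non-TEAEs appear only in the by-subject listing.

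**The concern.** Assigning an event of unknown timing to the drug is a sensible conservative default. The difficulty arises when the timing is in fact known: a stop date before first dose shows that the event was over before any drug was taken. The rule still gives it the first-dose date as onset, which creates a record that begins after it ended and counts as treatment-emergent.

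The trial has one arm, so no comparator carries the same misclassification, and the absolute frequencies and rates are the safety result. A false TEAE also enters the exposure-adjusted incidence rate (EAIR) numerator with essentially no time at risk, because that time runs from first dose to first onset.

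The SAP applies this kind of logic check elsewhere. Imputed AE stop dates may not pass the date of death (15.1), and an imputed end date of a prior DMD is truncated to the day before consent if it would fall later in that month (Section 12). The missing check here looks like an oversight.

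A second, conditional question is what happens to an AE that starts in screening and worsens after first dose, since the definition mentions onset only.

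**Working it through.** The documents give no figure to reproduce. The check applies the written rules to test dates and then shows the possible size under stated assumptions.

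**1. Rules as written.** Let S be the first-dose date.
- Imputed onset = S if the onset is wholly missing, or if its known month and year, or known year alone, equal those of S.
- Otherwise, a missing day or month = 1.
- TEAE if S ≤ onset ≤ end of Treatment Period.

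**2. Test dates**, assuming S = 20 March 2019:

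| Case | Recorded onset | Stop or course | Onset used | TEAE as written | TEAE with stop-date check |
|---|---|---|---|---|---|
| A | ?? March 2019 | stop 10 March 2019 | 20 March 2019 | yes | no |
| B | ?? ??? 2019 | stop 28 February 2019 | 20 March 2019 | yes | no |
| C | missing | stop 10 March 2019 | 20 March 2019 | yes | no |
| D | 5 March 2019 | worsens 25 April 2019 | 5 March 2019 | no | no |
| E | ?? February 2019 | stop 10 March 2019 | 1 February 2019 | no | no |

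In A and C the imputed onset is 20 − 10 = 10 days after the stop; in B it is 20 days after. Case E is handled correctly, so the fault lies only in the first imputation step. Case D is untouched by a stop-date check: it needs a worsening criterion or a new record dated 25 April.

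**3. Possible size.** Assumptions, none of them given as data: all 445 planned subjects are in the Safety Set; subjects without the event contribute 2 years, true cases 1 year on average and false cases 0.

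- Time at risk t = 2 × (445 − n) + 1 × (true cases), where n = true + false cases.
- EAIR per 100 subject-years = 100 × n / t, with the exact Poisson interval of SAP 15.1.1.

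| True + false | n/445 | t (years) | EAIR | 95% CI |
|---|---|---|---|---|
| 5 + 0 | 1.12% | 885 | 0.565 | 0.183–1.318 |
| 5 + 1 | 1.35% | 883 | 0.680 | 0.249–1.479 |
| 5 + 3 | 1.80% | 879 | 0.910 | 0.393–1.793 |
| 22 + 0 | 4.94% | 868 | 2.535 | 1.588–3.837 |
| 22 + 1 | 5.17% | 866 | 2.656 | 1.684–3.985 |
| 22 + 3 | 5.62% | 862 | 2.900 | 1.877–4.281 |

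One false case raises a 5-subject term by a fifth (6/5 = 1.20) and a 22-subject term by under 5% (23/22 = 1.045). The 22-subject row was chosen because it sits at the 5% threshold used in some AE tables, so it is a worst case for crossing that line.

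**The case against.** **The corner is narrow.** The event must begin and end in a window that is normally at most a month, with an incomplete onset but a stop date good enough to place it before dosing. Protocol 7.4.1.2 asks for complete AE data with onset and resolution dates, and the first scheduled AE assessment is at Baseline, when recall is recent. This stands, and it is why the number affected is probably small. Prolonged screening widens the window for some subjects, and the diary is issued only at Baseline, so it does not help date these events.

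**The error is conservative and visible.** It adds events to the drug's tally, imputed values are flagged in listings (SAP Section 9), and SOC/PT tables without the 5% threshold are also planned. The study is exploratory with descriptive safety summaries, and the illustrative shifts lie well inside the intervals shown. This too stands as a limit on importance. It does not justify an onset date later than its own stop.

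**Worsening may already be covered.** A reader might infer that screening AEs which worsen on drug are lost from the TEAE tables, and that these are the more important events. The documents do not establish this. Protocol 7.4.1.1 excludes from AEs only baseline conditions that do not worsen; 7.4.1.2 records unfavourable changes as AEs; 7.4.4 and SAP 15.5 send worsening abnormalities to AE reporting. If worsening opens a new record dated at the worsening, that record is a TEAE. The CRF completion conventions that would settle this are cited but not among the documents. What remains is that the derivation depends on a convention the SAP does not state.

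**Conclusion.** The first-dose imputation gives a wrong classification for one definable group: AEs whose onset is missing or partial (matching first dose) and whose stop date is known to precede first dose. Nothing else in the protocol or SAP corrects this. AEs with complete onset dates are classified correctly. The size cannot be computed because the documents give no count of partial dates. It is probably small, and its direction is towards more TEAEs.

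A reader might go further and conclude that TEAE frequencies and exposure-adjusted rates are wrong in both directions. That is not supported. The upward error requires that such records exist, and the downward error requires in addition that worsening is kept inside the screening record. Even in that case, all AEs and all SAEs are still listed, deaths are tabulated from the Study Termination page, and lymphocyte counts are graded from laboratory values independently of TEAE status (SAP 15.1.1, 15.2 and 15.3).

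The worsening gap is therefore a secondary, conditional point: such an AE is missed unless it is re-recorded as a new AE dated at the worsening.

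**What to change.** In SAP 15.1:

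1. Apply the first-dose imputation only if the stop date (recorded, or imputed to month end) is missing or is on or after first dose. Otherwise the AE is not treatment-emergent, and its imputed onset may not be later than its stop date. A stop date that Section 15.1 leaves unimputed is treated as missing, so events of truly unknown timing remain TEAEs.
2. Either add to the TEAE definition onset before first dose with worsening in severity or seriousness after it, or state that worsening opens a new AE record dated at the worsening.

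The cost is two sentences and a small change to one derivation, with no new data collection for the first item. Because the same rules serve the interim and final safety analyses, the clinical study report should note the change if interim tables were already produced under the present rule.

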15.1.1 All Adverse Events

TEAEs will be summarized using MedDRA (latest version available) preferred term (PT) as event category and MedDRA (latest available version) primary system organ class (SOC) body term as Body System category overall and by subgroups, DMD pre-treated and pre-treatment naïve.

Unless otherwise stated adverse events will be displayed in terms of frequency tables: PT and primary SOC in alphabetical order. Only the highest occurred severity of an TEAE by PT and subjects will be displayed in summary tables by severity.

Adverse events related to study treatment are those events with relationship missing, unknown or related.

The following overall frequencies of subjects with the corresponding TEAE will be prepared. In addition, the tables will be provided by PT and primary SOC in alphabetical order:

- Any AE,
- Any study treatment related AEs,
- Any serious AEs,
- Any non-serious AEs

- Any study treatment related serious AEs,
- Any AE by severity (mild, moderate, severe)
- Any study treatment related AE by severity (mild, moderate, severe)
- Any AEs leading to death (AEs with outcome “fatal”),
- Any study treatment related AEs leading to death (AEs with outcome “fatal”).

Summary table for non-serious adverse events applying frequency threshold of 5% will be provided by SOC and PT.

Summary tables for serious and non-serious adverse events applying frequency threshold of 5% sorted by decreasing frequency will be provided by PT.

All AE by worst severity (any severity, moderate or worse, severe) will be presented by SOC and PT.

All AEs including non-treatment emergent AEs will be listed by subject for the SAF.

Exposure Adjusted Incidence Rate

Exposure adjusted incidence rates (EAIR) are calculated as number of subjects with AE divided by the total time at risk, which is defined as a sum of the individual times in years of all subjects in the safety population from start of study medication to first onset of AE or end of treatment period, whichever occurs first. Total time at risk can be expressed also in 100 subject-years.

The exact Poisson 95% confidence intervals for the EAIR are calculated using the relationship between the Poisson and the Chi-square distribution (Ulm, 1990):

$$LCI = \frac{\chi_{2n, \frac{a}{2}}^2}{2 \times t},$$

$$UCI = \frac{\chi_{2(n+1), 1 - \frac{a}{2}}^2}{2 \times t},$$

where t is the sum of the individual times in years of all subjects and n is the number of subjects with a specific AE for the EAIR, which will be the basis for the number of the degrees of freedom for the chi-square quantile for the upper tail probability χ^2 .

Exposure adjusted incidence rates of TEAEs will be presented overall, and by SOC and PT.

The following table will be provided:

- Exposure adjusted incidence rates of AEs by SOC and PT.

15.1.2 Adverse Events Leading to Treatment Discontinuation

The following overall frequency tables will be prepared for the adverse event actions. Tables will be provided by PT and primary SOC in alphabetical order:

- Any AE leading to temporary discontinuation of study drug,
- Any AE leading to permanent discontinuation of study drug,
- Any AE leading to dose reduction of study treatment

15.2 Deaths, Other Serious Adverse Events, and Other Significant Adverse Events

15.2.1 Deaths

Any discontinuations due to death (see Section 10.1) and any AE leading to death will be tabulated (see Section 15.1.1).

A summary table of observed Deaths (from “Study Termination” eCRF page) will be provided together with TEAEs with fatal outcome by PT.

15.2.2 Serious Adverse Events

The statistical analysis and reporting of serious adverse events are defined in Section 15.1.1. In addition, all serious adverse events will be listed.

15.2.3 Other Significant Adverse Event

TEAEs associated to COVID-19

The frequency of TEAEs associated to COVID-19 will be presented. The relevant events will be identified based on the SMQ COVID-19 (narrow scope) and will be presented by SOC and PT.

Fatigue

The prevalence of fatigue will be presented for each month of the Course 1 Treatment Period and separately for each month of the Course 2 Treatment Period. The prevalence at a given month is defined as:

(Number of patients with fatigue during the month/ Number of patients with fatigue during the month or still in the study at the end of the month) * 100,
where patients with fatigue during the month are all patients who had at least one reported TEAE with PT equal to 'Fatigue' that either started during the month or is still ongoing from the previous month.

If the end date of the AE is partially or completely missing and the AE is not reported as ongoing, the end date will be imputed as follows:

- Day missing but month and year available: last day of the month,
- Day and month missing: last day of the year but not later than end of Treatment Period 2,
- Completely missing: end of Treatment Period 2

The results will be presented in a tabular as well as graphical manner. Course 1 and 2 Treatment Periods as well as duration of a month is defined in Section 9.

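### Monthly fatigue prevalence is shown by treatment course but divided by everyone still in the study, and late fatigue in subjects who never start Course 2 is in neither panel

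*SAP*

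**What the plan says.** SAP 15.2.3 singles out fatigue for a monthly prevalence table and graph, to be "presented for each month of the Course 1 Treatment Period and separately for each month of the Course 2 Treatment Period". The numerator is patients with "at least one reported TEAE with PT equal to 'Fatigue' that either started during the month or is still ongoing from the previous month". The denominator is "Number of patients with fatigue during the month or still in the study at the end of the month". Neither is expressly tied to the course that heads the panel.

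The course periods are defined subject by subject in SAP Section 9:

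- For someone who starts Course 2, the Course 1 period closes the day before the first Course 2 dose: "End = Start of study medication at or after the Month 12 Visit -1 day".
- Otherwise the rule is "if the subject did not receive Treatment Course 2: Start of study medication of Treatment Course 1 + 457 days", or study discontinuation if that comes first.
- The Course 2 period opens only with a Course 2 dose and closes with the overall Treatment Period, which runs to the Month 24 or early termination visit.

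Two general rules bear on this. SAP Section 7 keeps all data from both courses in safety analyses whatever the delay. SAP Section 9 adds: "For all other analyses (except efficacy) the data is not limited to the Course 1 Treatment Period for subjects with a Delayed Treatment Course 2". By the SAP's definition, a delayed Course 2 includes one that never started.

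**The concern.** A panel headed by Course 1 should describe patients who are in Course 1. From about month 12 onward the subjects still in that course are the late starters and never-starters, while the stated divisor also counts everyone who has moved to Course 2. A curve that drops for this reason could be read as fatigue resolving after the first course.

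Never-starters have a further problem. Protocol 5.5.1 and 5.5.2 keep subjects who stop the drug in scheduled visits to planned completion. SAP 15.1 counts their adverse events as treatment-emergent throughout the Treatment Period. Yet after their Course 1 period closes they belong to no panel. SAP Section 13 expects such subjects and tabulates them. They are also a selected group: the reasons for withdrawal from therapy in Protocol 5.5.1 include lymphopenia, infection, malignancy and a switch to another disease-modifying drug.

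**Working it through.** **1. The SAP's own figure.** 360 + 90 + 7 = 457 days, as stated. First dose is Day 1, so first dose + 457 days is Study Day 458, the last day of a never-starter's Course 1 period. That period is 458 days long: 458 / 30.4375 = 15.05 months, or 458 / 30 = 15.27 months.

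**2. Coverage by type of subject.** Protocol 7.1.7 allows Course 2 to be delayed by up to 6 months; with the visit window that is 360 + 180 + 7 = 547 days, and 547 / 30.4375 = 18.0 months.

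| Subject | Course 1 period ends | Course 2 period | Follow-up in neither |
|---|---|---|---|
| Starts Course 2 on time | day before Course 2 dose, about 360 days after first dose | to end of Treatment Period | none |
| Starts Course 2 late | day before Course 2 dose, up to about month 18 | to end of Treatment Period | none |
| Never starts Course 2 | first dose + 457 days | none | Study Day 459 to Month 24 |

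Only never-starters have a gap. Course 1 months beyond about 12 contain only the last two rows. With months of 30.4375 days, month 12 ends at day 365.25, after the nominal Course 2 start, so month 12 is slightly affected too.

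**3. Length of the gap.** Uncovered days = Month 24 offset − 457, for a never-starter who stays to Month 24. The share is of the whole Treatment Period (offset + 1 days).

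| Month 24, days after first dose | Uncovered days | Share |
|---|---|---|
| 713 (720 − 7) | 256 | 256/714 = 35.9% |
| 720 (24 × 30) | 263 | 263/721 = 36.5% |
| 727 (720 + 7) | 270 | 270/728 = 37.1% |
| 730 (about 24 × 30.4375) | 273 | 273/731 = 37.3% |

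**4. Effect of the denominator.** Take a Course 1 month after month 12. Let q be the share of subjects in the study who are still in Course 1, p1 the fatigue prevalence among them, and p2 the prevalence among those already in Course 2. The number in the study cancels.

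- Both parts restricted to Course 1: p1.
- Reading A, Course 1 numerator over everyone in the study: q × p1.
- Reading B, everyone over everyone: q × p1 + (1 − q) × p2.

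Illustration only, with assumed p1 = 10%, p2 = 5% and q from 5% to 30%; none of these is in the documents.

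| q | Restricted | Reading A | Reading B | Course 2 share of B |
|---|---|---|---|---|
| 5% | 10% | 0.5% | 5.25% | 4.75/5.25 = 90% |
| 10% | 10% | 1.0% | 5.5% | 4.5/5.5 = 82% |
| 20% | 10% | 2.0% | 6.0% | 4.0/6.0 = 67% |
| 30% | 10% | 3.0% | 6.5% | 3.5/6.5 = 54% |

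Under A the dilution factor is exactly 1/q. Under B the figure is mostly Course 2 fatigue across this range.

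**The case against.** The best defence is that the ratio should be read with its lead-in. Course periods are individual, a subject already in Course 2 has no month 14 of Course 1, and remaining in the study then works only as a dropout rule. That reading gives a sensible table, and it may be what was meant. The text does not say it, though. SAP 10.1 counts discontinuing medication and discontinuing the study separately. The Section 9 rule that treats delayed subjects as discontinued at the end of Course 1 is confined to efficacy analyses.

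It can also be said that the general safety rules do not oblige every display to cover all follow-up. That is fair as far as it goes. But nothing in SAP 15.2.3 says that the later follow-up of never-starters is left out on purpose.

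Three stronger conclusions that a reader might draw are not supported:

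- **Fatigue events are lost from safety reporting.** They are not. Fatigue after first dose + 457 days is still treatment-emergent and enters the tables, listing and exposure-adjusted rates in SAP 15.1.1.
- **The end-date imputation fails for never-starters.** The rule "Completely missing: end of Treatment Period 2" uses a label that Section 9 does not define. Read as the Course 2 period, its end is set equal to the end of the Treatment Period, and that date exists for every subject.
- **The Course 1 tail is understated by some fixed multiple.** Any such multiple only restates the assumed share still in Course 1. Protocol 8.5.1 expects substantial delay in a small number of subjects but gives no figure.

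**Conclusion.** The point holds on the literal text, for this one display. Course 1 months after about month 12 are mis-stated unless the denominator is read more narrowly than it is written. The direction depends on whether the numerator is limited to Course 1, and the size on a share the documents do not report. The Course 2 panel carries the same unrestricted denominator.

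The never-starter gap needs no such assumption. It follows from the period definitions and is about 256 to 273 days, or 36% to 37% of the Treatment Period, for each never-starter who stays to Month 24. How many there will be is unknown.

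The study is single-arm and exploratory, and the table is descriptive with no test or decision attached. This is a correction that should be made because the rule as written gives a misleading curve and the remedy is cheap; it does not threaten the trial's conclusions.

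**What to change.** In SAP 15.2.3:

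- Restrict numerator and denominator to subjects whose Course Treatment Period covers that month, and state how part-months count. Being in the period on any day of the month, applied to both, is workable. Merely replacing the study by the course in the present denominator would inflate the month in which most subjects leave Course 1, because leavers would be counted only if they had fatigue.
- Print the number at risk for every month of both panels.
- Show never-starters from Study Day 459 in a separate row or panel labelled as having no Course 2. Do not run them on as a continuation of the Course 1 curve, whose last months would then be a selected group.
- Name the month length. Section 9 gives both 30 and 30.4375 days; its conversion rule for observations other than visit dates points to 30.4375.
- Optionally, refer to the end of the Treatment Period in the end-date rule. This only tidies the wording, since the date is the same.

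The cost is a few lines of SAP text and a small programming change, with no new data. Late Course 1 months and the extra row will have small denominators and imprecise percentages.
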